 - Patient-reported comorbidities [hypertension (requiring or not requiring medication), diabetes mellitus (insulin or non-insulin dependent), coronary artery disease, myocardial infarction, congestive heart failure (with preserved or reduced ejection fraction, if known), pacemaker or AICD, asthma (with or without emergency department evaluation and / or hospital admission in the past year), chronic obstructive pulmonary disease, chronic bronchitis, chronic steroid use, history of transplant (with type),

MEDICAL PROTOCOL (HRP-590)

SHORT PROTOCOL TITLE: Randomized control trial of losartan for outpatients with COVID-19

VERSION DATE:5APR2020

arrhythmias including atrial fibrillation, dialysis, angina, pulmonary hypertension and obstructive sleep apnea, renal disease, liver disease, tobacco and alcohol use history, recent pregnancy or breastfeeding history, height and weight]

- Self-reported home medications [antihypertensives, insulin, non-insulin diabetes medications, corticosteroids (inhaled or systemic), other immunosuppressants hydroxychloroquine, other COVID-directed treatments] or home oxygen use
- Use of outpatient COVID-directed treatments (such as hydroxychloroquine, Tylenol, ibuprofen, azithromycin, or others)
- PROMIS Pool v1.0 Dyspnea Characteristics Survey (5 question Likert scale survey) (attached) with date/time of administration
- Short form 12 (SF-12) health survey (attached) with date/time of administration
- Oropharyngeal swab every third day (performed, yes or no)
- Lowest home blood pressure daily
- Highest home temperature daily
- Medication adherence
- Hospital admission (with date, if applicable)
 - a. If admitted: initial vital signs, initial and highest method of respiratory support (oxygen by nasal cannula, facemask, high flow nasal cannula, CPAP, BIPAP, endotracheal intubation, ECMO), initial and worst measures of organ failure (SOFA score), and initial and worst markers of cardiac injury (troponin, BNP/pro-BNP. CXR or CT chest results will be recorded. If patients are admitted to non-MHealth or HCMC hospitals, we will contact the patient to obtain permission to request data from their hospitalization.
- Date of death (if applicable)
- Study withdrawal, with date and time (if applicable)

- Final outcome follow-ups will be determined through a combination of patient report, electronic medical record review, and review of the social security death index (SSDI).

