3.0 Study Endpoints/Events/Outcomes

3.1 *Primary Endpoint/Event/Outcomes:* The primary endpoint is the need for hospital admission at 15 days from randomization.

3.2 *Secondary Endpoint(s)/Event(s)/Outcome(s):*

- Subjective improvement in dyspnea as measured by the dyspnea PROMIS measures (survey attached) at day 0, 4 and 10
- Daily maximum temperature
- Number of emergency department or clinic presentations within 28 days
- Disease severity rating on the *7-point ordinal scale* [Time Frame: Day 7, 15, 28]
 - The *7-point ordinal scale* is an assessment of the clinical status at the first assessment of a given study day. The scale is as follows: 1) Death; 2) Hospitalized, on invasive mechanical ventilation or extracorporeal membrane oxygenation (ECMO); 3) Hospitalized, on non-invasive ventilation or high flow oxygen devices; 4) Hospitalized, requiring supplemental oxygen; 5) Hospitalized, not requiring supplemental oxygen; 6) Not hospitalized, limitation on activities; 7) Not hospitalized, no limitations on activities
- Change in viral load by oropharyngeal swab
- Ventilator free days, oxygen free days
- Need for hospital admission and oxygen therapy at 15 days

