diseases. Specimens will be transported and processed by the University of Minnesota BSL-3 laboratory and frozen at -80 C until the time of analysis. Samples will be deidentified and labeled only with a patient ID number.

- ***Biospecimens and protocol deviations:*** Baseline clinical laboratory results will be required to establish inclusion and exclusion criteria, and missing data will be reported as protocol deviations. However, significant barriers exist to the collection and processing of other biospecimens due to the increased containment required, meaning that not every study site may be able to accomplish these procedures. In addition, patient self-collection will lead to missing samples. While every effort will be made to obtain these biospecimens, failure to do so will not constitute protocol deviations.
- ***Specimen sharing:*** Requests for specimen sharing during or following study completion for sharing will be evaluated by a steering committee that will be established and will include the principal investigators. Requests will be evaluated on a case-by-case basis. If specimens are shared, human genetic analysis will only proceed on those patients who opt-in to genetic testing. Genetic testing of viral genomes will be allowed to proceed on all patients.

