15.0 Statistical Considerations

- 15.1 *Data Analysis Plan:* All analysis will focus on comparisons between the treatment and control groups. Demographics and other baseline clinical characteristics will be summarized using descriptive statistics. Descriptive statistics will be presented by treatment group using mean, standard deviation, median, and interquartile range (IQR) for continuous variables and frequencies and percentages for categorical variables. The primary outcome, hospitalization at day 15, will be summarized by group using the sample proportion with 95% asymptotic confidence intervals. Treatment groups will be compared using the Chi-square test and the treatment

effect will be summarized by the absolute difference in the hospitalization rate between groups. Secondary endpoints will be summarized by the mean and standard deviation and compared using the two-sample unequal variance t-test, potentially after appropriate data transformations to assure that assumptions of the t-test are met. Time-to-event endpoints will be summarized by Kaplan-Meier curves and compared using Cox proportional hazards regression. For all endpoints, we will complete secondary analyses comparing for important baseline variables that are unequally distributed between treatment groups. Preplanned subgroup analyses are planned by age (dichotomized at 50 and by decade), history of hypertension, sex, and smoking history, timing of randomization from symptom onset, and respiratory support needed at the time of randomization. In addition, we will perform a preplanned pooled analysis with a planned national outpatient trial of losartan versus placebo targeting the same patient population with harmonized assessments and outcomes.

15.2 *Power Analysis:* Previously published literature from China suggest a 15% hospitalization rate for patients infected with coronavirus.^{7,30} To detect a difference in hospital admission rate of 15% in control vs. 7% in the intervention group, with alpha of 0.05 and 80% power using a two-sided test, we will need 264 patients in each group. We will enroll a total of 290 patients in each group (total sample size of 580) to account for the possibility of 10% loss-to-follow-up.

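### Viral load is compared as an unadjusted change score; pre-specifying the baseline swab as a covariate would be at least as precise, at no data cost

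*Combined protocol and SAP*

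**What the plan says.** Section 3.2 lists "Change in viral load by oropharyngeal swab" among the secondary endpoints. It names no follow-up day, measurement scale or way of combining serial swabs.

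Section 15.1 gives one rule for these endpoints: "Secondary endpoints will be summarized by the mean and standard deviation and compared using the two-sample unequal variance t-test", with the qualification "potentially after appropriate data transformations to assure that assumptions of the t-test are met". It makes one provision for covariates, covering all endpoints: "we will complete secondary analyses comparing for important baseline variables that are unequally distributed between treatment groups". Baseline viral load is not mentioned there, and neither ANCOVA nor a mixed model is specified for viral load.

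Section 1.6 schedules a swab every third day. Sections 1.5 and 5.3 have swabs delivered by courier with the study drug, after randomization. Section 6.2 expects that "patient self-collection will lead to missing samples". Section 4.6 allocates 1:1, stratified by site and age.

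**The concern.** Subtracting baseline fixes the slope of follow-up on baseline at 1. Unless the true slope is close to 1, the subtraction carries baseline noise into the outcome. A model with baseline as a covariate estimates the slope instead. In large samples with 1:1 allocation it is never less precise than the change score, whatever the correlation or SDs.

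In a given trial, a chance difference in baseline viral load between arms also moves the change-score estimate. The strata do not include illness stage, and entry is allowed up to 7 days from symptom onset, so such differences can occur.

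What is at stake is the precision of one secondary comparison. A change score cannot be computed without a baseline value, so everyone in the planned t-test already has the covariate.

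**Working it through.** **Figures in the plan.** There is no sample size, power, SD or correlation for viral load. The only sample-size figure concerns hospitalization: "with alpha of 0.05 and 80% power using a two-sided test, we will need 264 patients in each group". For 15% versus 7%, the two-proportion formula gives 239 per group uncorrected and 264 with continuity correction, so 264 reproduces. It is used below only as an illustrative n.

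**Inputs.** rho is the correlation between baseline and follow-up viral load on the analysis scale. k is follow-up SD divided by baseline SD. Both are assumptions.

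**Step 1: variances, in units of the baseline variance.**
- Change score: 1 + k² − 2·rho·k
- Baseline-adjusted follow-up: k²(1 − rho²)
- Information lost by the change score: 1 − k²(1 − rho²)/(1 + k² − 2·rho·k) = (1 − rho·k)²/(1 + k² − 2·rho·k)

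The loss is never negative, and is zero only when rho·k = 1.

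**Step 2: equal SDs (k = 1).** The variance ratio is (1 − rho²)/[2(1 − rho)] = (1 + rho)/2, so the loss is (1 − rho)/2: 40% at rho 0.2, 35% at 0.3, 25% at 0.5, 15% at 0.7, 10% at 0.8 and 5% at 0.9. Simulation (2,000 runs, 264 per arm) gave 39%, 24% and 16% at rho 0.2, 0.5 and 0.7.

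**Step 3: unequal SDs.** Loss by the general formula:

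| k | rho 0.2 | rho 0.5 | rho 0.7 |
|---|---|---|---|
| 0.5 | 77.1% | 75.0% | 76.8% |
| 0.75 | 57.2% | 48.1% | 44.0% |
| 1 | 40.0% | 25.0% | 15.0% |
| 1.25 | 27.3% | 10.7% | 1.9% |
| 1.5 | 18.5% | 3.6% | 0.2% |

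The change score is less precise than ignoring baseline when 1 + k² − 2·rho·k > k², that is, when rho < 1/(2k). The threshold is 0.5 at k = 1 and 0.33 at k = 1.5.

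**Step 4: power, equal SDs.** Take an effect that the change-score test detects with 80% power (two-sided 0.05). Adjusted power is Φ[(0.842 + 1.960)/√((1 + rho)/2) − 1.960]:
- rho 0.3: 2.802/√0.65 − 1.960 = 1.515, power 94%
- rho 0.5: 2.802/√0.75 − 1.960 = 1.276, power 90%
- rho 0.7: 2.802/√0.85 − 1.960 = 1.079, power 86%

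This anchor implies a different effect size at each rho. With 264 per arm and an assumed true difference fixed at 0.25 follow-up SD, power goes from 62% to 83% at rho 0.2, from 82% to 91% at 0.5, and from 96% to 98% at 0.7.

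**Step 5: chance imbalance.** If the arms differ by D at baseline, the change-score estimate subtracts D and the adjusted estimate subtracts rho·k·D. They differ by (1 − rho·k)·D, which is half of D at rho 0.5 and k = 1. D averages zero over randomizations.

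**The case against.** The strongest reply is that the planned test is sound and the gain may be small. Much of that stands.

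- **Validity.** A reader might infer that a t-test on change is biased through regression to the mean. It is not: under randomization it is valid and unbiased, and imbalance matters only conditionally on the arms drawn.
- **Scale.** A reader might infer that untransformed values will be compared. Section 15.1 allows transformation, so a log scale is already open. Transformation does not alter the slope fixed at 1.
- **Existing adjustment.** Section 15.1 has an adjusted secondary analysis and a subgroup analysis by time from symptom onset. These partly answer the imbalance argument. But the adjustment depends on observed imbalance, does not name baseline viral load, and recovers no precision when the arms happen to be balanced.
- **Endpoint wording.** A change endpoint does not rule out adjustment. Change regressed on arm and baseline gives the same treatment estimate as follow-up regressed on arm and baseline. Only the general sentence in 15.1 needs to change for this endpoint.
- **Missing swabs.** The losses expected in section 6.2 might seem to favour adjustment. A single-day ANCOVA needs the same two swabs as the change score; only a repeated-measures model could use participants with some follow-up swabs missing.
- **Weight.** Section 3.3 says the trial aims at lung injury rather than the virus, and section 3.4 does not discuss viral load. The PROMIS dyspnea score falls under the same t-test, so the argument is not peculiar to viral load.

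**Conclusion.** The point holds as a free gain in precision for one secondary endpoint. The direction is firm: in large samples with 1:1 allocation, baseline adjustment is never less efficient than the planned comparison.

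The size is not firm. It would be tempting to quote a fixed loss of 15–40%, but that range needs equal SDs and rho between 0.7 and 0.2, and the documents supply neither. Over the same correlations the loss is about 0–19% at k = 1.5, 2–27% at k = 1.25, 44–57% at k = 0.75 and 75–77% at k = 0.5. The power figures of 94%, 90% and 86% likewise assume equal SDs and an effect set at 80% power for the change score. The primary result is not affected.

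**What to change.** In section 15.1, replace the t-test for viral load with a named model:

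- **Outcome:** log10 viral load, or change in it, at one named follow-up day (ANCOVA), or all scheduled follow-up swabs in a repeated-measures model.
- **Covariate:** baseline log10 viral load, pre-specified and included whether or not the arms look balanced.
- **Baseline:** the swab collected before the first dose. This needs stating because swabs and drug are delivered together after randomization.
- **Detection limit:** a stated rule for values below it.
- **Report:** the baseline-adjusted difference between arms with its confidence interval.

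The cost is a few sentences in 15.1. It needs no new swabs, visits or participants, and changes neither the primary test nor the sample size. The baseline and detection-limit definitions would be needed for the planned change score too.

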4.0 Study Interventions / Interventional Agents

4.1 *Intervention arm:* The intervention is losartan, an angiotensin receptor blocker, in microcrystalline methylcellulose, administered at 25 mg PO twice daily for 10 days (patients with eGFR 30-60 mL/min/1.73 m² will be given 25 mg once daily) or until hospital admission, whichever comes first.

- *Rationale for the duration of the intervention:* The average time from symptom onset to hospitalization based on reports to date is 8-9 days.^{7,31} We expect participants to present with at least 1-2 days of symptoms. We expect most participants to reach their primary endpoint within 10 days of treatment (11-12 days from symptom onset), which represents our time of maximal efficacy of the intervention in this cohort. We have chosen to stop treatment at the time of hospitalization as the participant may or may not be admitted to a participating hospital, introducing significant logistical limitations.
- *Rationale for the dose of treatment:* The lowest dose of losartan is 25 mg orally, which minimize risk of side effects and AEs to the patient. The maximum clinical dose is 100 mg daily. Losartan has a half-life of 2 hours with an active metabolite E3174 of 6-9 hours. The threshold for blockade of angiotensin-II receptor is at least 20 mg per day.³² Twice daily dosing has been shown to potentiate angiotensin-II receptor blockade compared with once daily dosing. We propose a dose of 25mg twice daily. At this dose, extrapolated data suggest 37% inhibition of angiotensin-II receptors, which we believe represents an excellent risk: benefit ratio for trial participants. At the highest maximum allowable clinical dose (50 mg twice daily) we would anticipate 50% inhibition of angiotensin-II receptor.³² Multiple early pharmacokinetic studies of losartan at the low-dose demonstrates the drug has minimal side effects on blood pressure (consistently <10 mmHg reduction in maximal systolic blood pressure) in healthy patients³³⁻³⁶ without an overactive renin-angiotensin-aldosterone system. Clinical exclusion criteria has been added to identify patients who might be at increased risk for side effects. Patients with moderate renal dysfunction (eGFR 30-60 mL/min/1.73 m² will be given 25 mg once daily given impaired renal clearance.

4.2 *Placebo arm.* Placebo capsules will match, and contain microcrystalline methylcellulose only.

4.3 *Investigational new drug.* The study will undergo pre-IND review with the Food and Drug Administration to determine the need for an investigational new drug assessment, and will be assigned an IND number if required.

4.4 *Timing of the intervention:* Treatment will continue for 10 days or attainment of the primary outcome (hospital admission).

4.5 *Duration of study participation:* The final follow-up will occur at 90 days after randomization to determine episodes of delayed hospitalization. Data analysis is expected to be completed within 1 year of enrollment of the final patient.

4.6 *Drug Handling, blinding, and randomization:*

Fairview Investigational Drug Services (IDS), part of M Health Fairview will oversee the preparation of treatment drug and placebo. Identical pills (#20) will be placed in identical

MEDICAL PROTOCOL (HRP-590)

SHORT PROTOCOL TITLE: Randomized control trial of losartan for outpatients with COVID-19

VERSION DATE:5APR2020

bottles with a deidentified study number coded by site and patient number (e.g. 01-001, 02-001, etc.). A site-specific randomization schema will be created (each site will undergo permuted block randomization with random block sizes stratified by site and age). Given significant differences in outcome by age, patients will be randomized by age strata (≥ 50 , < 50). Randomization allocation will be 1:1. IDS will not be blinded to patient randomization. All other members of the study, the participants, and the clinical care team will be blinded to treatment allocation.

4.7 *Provision of study drug to patients*: Following randomization, a courier service will ship drugs to study participants within 24 hours of randomization. Each dispensing will contain 20 capsules, enough to complete the 10-day therapy

4.8 *Study unblinding*: MHealth Fairview, East bank Inpatient Pharmacy UMMC campus, will hold the blind for all subjects on study. In the event of an emergency and unblinding is necessary, study staff can contact [contact], option 1, then option 2. This information is included on each label.

4.9 *Biosafety*: N/A. The intervention is not a biohazard.

4.10 *Stem Cells*: N/A

4.11 *Fetal Tissue*: N/A

4.12 *Use of radiation*: N/A

4.13 *Use of Center for Magnetic Resonance Research*: N/A

5.0 Procedures Involved

5.1 *Screening*: Screening logs containing non-identifiable information (age, gender, race, ethnicity, location of presentation, and reason for exclusion) will be maintained for patients screened but not enrolled. Patient screening will follow one of two screening procedures based on the location of their presentation.

- *Emergency department or COVID-specific clinic patients*: Initial pre-screening to determine study eligibility will necessarily proceed under waiver of informed consent and waiver of HIPAA authorization through the screening of electronic medical records by delegated members of the research team in participating emergency departments. Providers may contact study personnel to conduct pre-screening, as well. If the patient appears to be eligible based on pre-screening, and if acceptable to the treating physician, the patient will be approached by a study investigator or delegated study coordinator or research nurse to determine eligibility criteria. Patients seen in the emergency department but whose test results did not result prior to discharge will be given a study brochure with information to contact the study team if their test results positive and they wish to be considered for study participation. In addition, each site has clinical staff to call and alert patients regarding positive test results. These staff will alert the patient that they are eligible for a research study and that they may be contacted by study personnel, and will be given the opportunity to opt-out of this research contact. Once contact has been made, study personnel will conduct a screening questionnaire to determine eligibility criteria.

MEDICAL PROTOCOL (HRP-590)

SHORT PROTOCOL TITLE: Randomized control trial of losartan for outpatients with COVID-19

VERSION DATE:5APR2020

- **Drive-thru clinical patients:** M Health Fairview will have 4 drive thru centers for SARS-CoV-2 screening. Patients presenting to one of the centers will be given a brochure informing them that if they test positive and are interested in enrolling in a clinical trial of a new treatment for COVID-19 to contact our study coordinators (see attached study related materials). Once contact has been made, study personnel will conduct a screening questionnaire to determine eligibility criteria.

- **Dashboard:** In addition, participating sites have an electronic dashboard or electronic-medical record based report of all pending and confirmed positive COVID-19 tests that can be used for real-time prescreening of emergency department or COVID-clinic patients.

5.2 **Enrollment:** Patients or their legally authorized representative, with due consideration of vulnerable patient populations, (see section 9) will be eligible for consent by delegated members of the study team with appropriate training and experience in the conduct of human subjects research. Enrollment will similarly occur via one of two methods based on location of identification. **In all cases, consent conversations will occur via telemedicine, institutionally approved video connection platform, or phone call (drive through patients or ED patients discharged prior to randomization) which limit traditional face-to-face contact.** If the participant regains capacity to consent, we will reconsent the participant in the study. If they decline, further study procedures will stop but previously collected data under the LAR consent will be utilized. If the participant does not regain capacity to consent, study procedures will continue under consent of the LAR.

- **Rationale for the use of telemedicine, video connection, or phone consent:** We have chosen this method of consent *in order to minimize risk to research team and healthcare providers, and to decrease community spread of the disease.* We have prior experience using telemedicine and phone consent coupled with electronic consent form review for time-sensitive clinical trials of stroke. While the *rationale* for eConsent is different in this case (minimization of disease spread during a pandemic), we believe it is *appropriate* for the disease and intervention being studied. LARs will not be used for remote consent. Critically, the low-dose and established safety profile of losartan, with multiple studies demonstrating minimal side effects on blood pressure in healthy patients³³⁻³⁶ without an overactive renin-angiotensin-aldosterone system, combined with the close remote follow-up methods proposed in this study make the risk: benefit ratio for the alteration of traditional consent process acceptable for participants, providers, and the public.

- **Emergency department or COVID-clinic patients (patient is still in the emergency department or clinic):** For the sake of healthcare provider safety, and to minimize the spread of the virus, this visit will occur via a HIPAA compliant telemedicine consultation using tablets with telemedicine capabilities housed in the emergency department or with the study team. At this visit, consents will be reviewed in detail with the subject or LAR. The subject or LAR will have the opportunity to ask questions. If the patient (or LAR) agrees to become a study participant, electronic consent will be obtained using HIPAA and rule 11 compliant

MEDICAL PROTOCOL (HRP-590)

SHORT PROTOCOL TITLE: Randomized control trial of losartan for outpatients with COVID-19

VERSION DATE:5APR2020

electronic consent, stored and maintained in a secure RedCap server (see departmental policy on eConsent, attached).

- *Non-emergency department or COVID-clinic patients (patient returned home) or drive-thru clinic patients: For the sake of healthcare provider safety, and to minimize the spread of the virus, pre-screening and consent will occur through a video connection or phone call.* At this visit, consents will be reviewed in detail with the potential participant. The potential participant will have the opportunity to ask questions. If the participant agrees to become a study participant, electronic consent will be obtained using HIPAA and rule 11 compliant electronic consent, stored and maintained in a secure RedCap server (see departmental policy on eConsent).
- Eligible patients who meet inclusion criteria but do not have a documented creatinine and blood pressure reading within 7 days of the return of their positive COVID19 test results will undergo remote consent and enrolled. However, prior to randomization they will be required to participate in additional study screening at a clinic location prepared to accept known COVID-19 positive patients. The additional screening procedures will include: a blood pressure, creatinine, and potassium.

5.3 *Administration of study drug:* Patients will be given prepared components necessary for conduct of the study, including study drug (losartan or placebo), a thermometer, a home blood pressure cuff, and oropharyngeal swabs shipped supplies via same-day courier service.

5.4 *Patient follow-up:* Participants will receive phone calls by trained study personnel every other day for the 10 days of the intervention period to monitor for the development of complications including lowest daily blood pressure (measured at least once by home blood pressure cuff provided to the patient and medication compliance. Data will be documented into a Redcap database. The coordinators will have participants complete 2 qualitative surveys at enrollment, day 4, and day 10 (both attached in supplement). Surveys and adverse event assessments conducted within 1 day of the time point will be counted as qualifying and not considered missing. At day 15 (+/- 2 day), patients will be asked to return for repeat research blood draw to include creatinine testing. Patients will be contacted by phone at day 28 (+/- 3 days) and 90 (+/- 3 days) for short and intermediate term outcomes. If there is no follow-up due to lack of patient response, this will be documented and not counted as a protocol deviation.

MEDICAL PROTOCOL (HRP-590)

SHORT PROTOCOL TITLE: Randomized control trial of losartan for outpatients with COVID-19

VERSION DATE:5APR2020

5.5 *Table of events:*

		Study Day																			
	Screening / Enrollment ^{t*}	1	2	3	4	5	6	7	8	9	10	11	12	13	14	15	28	90			
ELIGIBILITY																					
Covid-19 Result confirmation	X																				
Inclusion / Exclusion	X																				
Informed Consent	X																				
ADDITIONAL POST-ENROLLMENT PRESCREENING (IF NOT ALREADY AVAILABLE)																					
Pregnancy assessment and birth control X plan**	X																				
Blood Pressure within 1 week of randomization	X																				
Creatinine / Potassium within 1 week of randomization	X																				
Randomize subject if eligible after additional prescreening	X																				
POST-RANDOMIZATION																					
Demographics	X																				
Medical History / CRF	X																				
Dispense / administer study drug**	X	X	X	X	X	X	X	X	X	X	X										
STUDY PROCEDURES (while outpatient) #																					
Assessment of Hospitalization			X		X		X		X		X								X	X	
Adverse event assessment			X		X		X		X		X								X	X	
Review adherence			X		X		X		X		X										
Review and record blood pressures and temperatures			X		X		X		X		X										
PROMIS Survey					X							X							X		
Short Form 12 Health Survey						X						X							X		
Oropharyngeal swabs	X			X		X			X		X										
Potassium / Creatinine Check																			X		
Follow-up biospecimens (OP swab + blood draw)																		@			
Electronic medical record / death index review																			X		

*Within 72 hours of + COVID-19 test results,

**In women of child-bearing age, patients must confirm negative test with study personnel prior to beginning treatment as well as confirmation of acceptable birth control method. For those capable of having children, a pregnancy test will be delivered to patients to confirm no pregnancy prior to initiation of study drug.

#Outpatient follow-ups +/- 1 day are accepted.

@ We will attempt to obtain oropharyngeal and blood biospecimens from patients hospitalized when they would otherwise have been planned

